3.3.2 Observation indicators

3.3.2.1 Primary Outcomes

Incidence of AKI within 7 days postoperatively

Percentage of subjects who developed new-onset AKI within 7 days postoperatively. AKI diagnosis was determined by clinicians who remained blinded to group assignments, based on the criteria established by the Global Outcomes in Kidney Disease (KDIGO) standards, as specified below (meeting any one criterion suffices):

1) Serum creatinine elevation $\geq 26.5 \mu\text{mol/L}$ within 48 hours; 2) Increase ≥ 1.5 -fold from baseline within 7 days; 3) Urine output reduced to $<0.5 \text{ mL/kg/h}$ for 6 consecutive hours.

Baseline creatinine was defined as the most recent preoperative serum creatinine measurement.

After baseline creatinine levels were obtained, serum creatinine and urine output were measured daily for seven consecutive days postoperatively.

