3.3.2.2 Secondary Outcomes

1) Severity of AKI

Within 7 days postoperatively, the postoperative AKI classification was assessed according to KDIGO criteria based on AKI severity (KDIGO staging: Stage 1/2/3):

Stage 1: Serum creatinine elevation ≥ 0.3 mg/dl or 1.5 – 1.9 times the baseline value, or urine output < 0.5 mL/(kg · h) for 6 – 12 hours;

Stage 2: Serum creatinine levels increased 2.0 – 2.9-fold, or urine output < 0.5 mL/(kg · h) for ≥ 12 hours;

Stage 3: Serum creatinine elevation ≥ 3.0 mg/dl, or ≥ 3 times the baseline value, or urine output < 0.3 mL/(kg · h) for ≥ 24 hours, or requiring RRT.

The AKI severity grading was determined by the highest KDIGO stage achieved within 7 days postoperatively.

2) Renal replacement therapy

The proportion and duration of acute RRT required during hospitalization.

3) Renal function recovery

In patients with AKI, those who still meet AKI criteria on postoperative day 7 were defined as having persistent AKI. The time from diagnosis to the first recovery of serum creatinine to within 1.5 times the baseline level without the need for RRT was calculated as the creatinine recovery time.

4) Long-term renal function

Serum creatinine and eGFR at 30 days postoperatively.

5) Autonomic nervous function

5-minute electrocardiogram (ECG) signals were collected preoperatively and at 24 hours, 48 hours, and 72 hours postoperatively, with heart rate variability (HRV) analyzed using Kubios HRV software.

6) Early recovery quality

Postoperative early recovery quality was systematically evaluated from multiple dimensions. Mechanical ventilation duration was defined as the time from the first successful extubation after surgery. The vasoactive drug index was calculated daily within 7 days postoperatively, with peak values and mean values recorded separately. Delirium incidence was assessed daily using either

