The proportion of patients requiring RRT during hospitalization was compared between groups using χ^2 test or Fisher's exact probability method; the duration of RRT was compared between groups based on its distribution characteristics using independent samples t-test or Mann-Whitney U test.

The proportion of patients with persistent AKI was compared between groups using the χ^2 test; the time to renal function recovery was plotted as cumulative recovery curves using the Kaplan-Meier method, with intergroup comparisons performed via the log-rank test. Patients who did not recover during the observation period were treated as censored data.

Serum creatinine and eGFR at 30 days postoperatively were compared between groups using independent samples t-test or Mann-Whitney U test based on their distribution characteristics.

HRV was analyzed using generalized estimating equations, with grouping, time points, and their interaction terms included as fixed effects. The optimal working-related matrix structure was selected based on the quasi-likelihood independence criterion. Significant group \times time interaction terms indicated statistically distinct temporal trends in HRV metrics between the two groups.

The duration of mechanical ventilation, peak/mean values of vasoactive drug index, peak/mean values of postoperative 48-hour pain NRS scores, and total opioid consumption were compared between groups using independent samples t-test or Mann-Whitney U test based on

their distribution characteristics. The incidence of delirium was compared between groups using χ^2 test. MMSE, QoR-15, and RCSQ were analyzed using generalized estimating equations (GEE), with model specifications identical to those used for HRV analysis.

The incidence rates of new-onset atrial fibrillation, pulmonary infection, stroke, and 30-day all-cause mortality were compared between groups using χ^2 test or Fisher's exact probability method. If the number of events was sufficient, Cox proportional hazards regression model could be employed for analysis, with adjustment for covariates when necessary. Hazard ratios (HR) and their 95% CI were reported.

Hospitalization duration and ICU stay duration were treated as continuous variables, which were expected to follow a skewed distribution. Between-group comparisons were performed using the Mann-Whitney U test. The re-admission rate due to complications was compared using the χ^2 test.

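### Creatinine recovery is timed to 1.5 times baseline, but two of the three AKI criteria can be met below that line, leaving recovery time zero or undefined for those patients

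*Combined protocol and SAP*

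**What the plan says.** Section 3.3.2.1 (Primary Outcomes) gives three AKI criteria and adds that "meeting any one criterion suffices". They are an absolute creatinine rise of at least 26.5 µmol/L in 48 hours, a relative rise ("Increase ≥ 1.5 -fold from baseline within 7 days"), and urine output below 0.5 mL/kg/h "for 6 consecutive hours". Baseline is the latest preoperative value. Creatinine and urine output are measured daily for seven days after surgery.

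Section 3.3.2.2, item 1, also lets a patient enter staging on the absolute rise alone: "Stage 1: Serum creatinine elevation ≥ 0.3 mg/dl or 1.5 – 1.9 times the baseline value".

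Section 3.3.2.2, item 3, contains two measures. Creatinine recovery time is: "The time from diagnosis to the first recovery of serum creatinine to within 1.5 times the baseline level without the need for RRT". For the day-7 status, among patients with AKI, "those who still meet AKI criteria on postoperative day 7 were defined as having persistent AKI".

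Section 3.3.3 analyses recovery time by Kaplan-Meier and log-rank. Its one special rule is: "Patients who did not recover during the observation period were treated as censored data". It does not restrict the analysis to patients who exceeded 1.5 times baseline, has no rule for a recovery time of zero, and does not mention death in this analysis.

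**The concern.** A time-to-recovery endpoint needs every patient to start in the unrecovered state. Here, entry is by any of three criteria and exit is by one creatinine line, and a patient can enter while already on the recovered side of it. For such a patient the recovery time carries no information about recovery; it records only which criterion triggered the diagnosis.

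The comparison between arms is exposed as well. The trial plans to study AKI severity. If stimulation shifted cases towards milder forms diagnosed below 1.5-fold, the zero times would collect in that arm and look like faster recovery. If those patients were instead left out as undefined, the analysed subset would differ between arms for the same reason.

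Separately, if a patient who dies unrecovered is censored, the Kaplan-Meier method treats that patient as still able to recover and so overstates cumulative recovery.

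**Working it through.** **1. The plan's own figure, used only to size the AKI subset.** Section IV gives 17.1% against 37.9%, two-sided α 0.05, power 0.80, 68 per group, and 76 per group after 10% dropout. With unpooled variance:

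n = (1.960 + 0.842)² × (0.171 × 0.829 + 0.379 × 0.621) / (0.379 − 0.171)² = 7.85 × 0.3771 / 0.04326 ≈ 68.4, so 69.

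This is within one patient of 68, and 68/0.9 = 75.6 rounds up to 76. Nothing below depends on that difference.

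Expected AKI cases: 76 × 0.171 = 13.0 and 76 × 0.379 = 28.8, together 41.8, or about 42 of 152.

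**2. Absolute-rise criterion against the recovery line.** Let b be baseline creatinine and suppose the 48-hour rise starts at b. A rise of exactly 26.5 gives the ratio (b + 26.5)/b, which is below 1.5 if and only if b > 26.5/0.5 = 53 µmol/L. Above that baseline, any rise of at least 26.5 but less than 0.5b is AKI and already below 1.5-fold.

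| Assumed baseline (µmol/L) | Minimum ratio at diagnosis | Rises that are AKI but below 1.5-fold (µmol/L) |
|---|---|---|
| 60 | 1.44 | 26.5 to under 30 |
| 80 | 1.33 | 26.5 to under 40 |
| 100 | 1.27 | 26.5 to under 50 |

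These ratios are minima for a rise that starts at baseline. With daily sampling the diagnostic value may overshoot, possibly past 1.5-fold. If the 48-hour rise starts from a postoperative value below baseline, the ratio can be lower, and the problem can then arise at baselines under 53 as well.

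**3. Urine-output criterion.** It has no creatinine condition. A patient can reach Stage 2 or Stage 3 by urine output alone with creatinine below 1.5-fold throughout.

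**4. One patient followed through the rule.** Take baseline 80 (assumed), so the line is 120. A rise to 106.5 within 48 hours is AKI at 1.33-fold. The first creatinine within 1.5-fold is the diagnostic value itself, so recovery time is zero. If creatinine then reaches 160 (2.0-fold, Stage 2), the patient remains recovered, because only the first qualifying value counts. If recovery instead requires an earlier value above the line, a patient who never crosses 120 has no recovery time.

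**5. Overlap with persistent AKI.** Day-7 status uses all the criteria, so a patient recovered at time zero can be persistent on day 7 through oliguria, a fresh 48-hour rise, or a late crossing of 1.5-fold.

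**6. Size.** The documents give neither a baseline creatinine distribution nor a split of AKI by criterion. With an assumed share f, the same in both arms:

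| f | Already below 1.5-fold at diagnosis (f × 41.8) | Remaining with a positive time |
|---|---|---|
| 20% | 8.4 | 33.4 |
| 40% | 16.7 | 25.1 |
| 60% | 25.1 | 16.7 |
| 80% | 33.4 | 8.4 |

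On the time-zero reading, the pooled median recovery time is zero once f exceeds one half.

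**The case against.** A reader might infer that most AKI patients are recovered at diagnosis and that the log-rank test mainly reflects the triggering criterion. The documents do not support that. They show that it can happen, not how often, and the 20% to 80% range is an assumption.

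Recovering to within a line can fairly be read as having first been above it. The gap is then an unstated analysis population instead of a set of zero times. This reading stands as possible, but it still leaves the endpoint undefined for the affected patients.

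A reader might also infer that the two halves of the outcome contradict each other. That goes too far. One is a first event on creatinine alone, and the other is a status on day 7 under all criteria. A patient may recover and relapse under any consistent threshold. The overlap is also narrower than it looks: a patient who rises by 26.5 µmol/L and then stays level has no 48-hour rise on day 7 and does not meet that criterion then. What remains is that the two measures use different standards, so some overlap comes from the definitions and not from relapse.

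Finally, this is one part of one of nine secondary outcomes, within the AKI subset. That limits its weight but not its correctness. On deaths, censoring is an inference from the wording of section 3.3.3, and the number affected is unknown.

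**Conclusion.** The mismatch is real, and nothing elsewhere in the document resolves it. Only the 1.5-fold criterion guarantees a start at or above the recovery line. The other two allow a recovery time that is zero or undefined, and on the time-zero reading a patient who later worsens stays recovered. That the rule can do this follows from the plan's own definitions. How many patients it touches does not: about 8 to 33 of 42 rests on the pilot AKI rates holding, on 76 patients per arm, and on an assumed share of 20% to 80% that is equal in the two arms. The direction of any bias between arms cannot be derived from the documents. The recovery curve and log-rank test should not be run on the definition as written. The primary endpoint and the sample size are unaffected.

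**What to change.** Before unblinding, amend section 3.3.2.2, item 3, and the matching paragraph of section 3.3.3:

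- **Recovery.** Define it as the first daily assessment after diagnosis at which creatinine is below 1.5 times baseline and less than 26.5 µmol/L above baseline, the urine-output criterion is not met, and there is no RRT. State that the 26.5 µmol/L limit above baseline is the chosen recovery counterpart of the 48-hour criterion. It is not that criterion itself, since a patient who stays level above the limit no longer shows a 48-hour rise.
- **Persistent AKI.** Judge day-7 status by the same definition, and say that a patient may recover and later relapse, so the two measures are not exact complements.
- **Confirmation.** Either require no sustained recovery, or require it and state that recovery first seen on day 7 is accepted without confirmation, because daily measurement ends there.
- **Death.** Treat death before recovery as a competing event and report cumulative incidence instead of censoring it.

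The cost is wording and a little more analysis work. Daily creatinine and urine output are already collected. Recovery times will look longer than under the present rule.

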3.3.2.3 Basic Clinical Indicators

Prior to randomization of patients, trained investigators collected the following baseline data. All measurements were based on the most recent test conducted after hospital admission and prior to surgery, and must be completed before randomization.

Demography and anthropometry: age, gender, height, weight, body mass index (BMI), ASA classification.

Cardiac function and risk scoring: NYHA cardiac function classification, left ventricular ejection fraction, EuroSCORE II score, Cleveland Clinic score, history of cardiac surgery, recent myocardial infarction (MI) history (<3 months).

Clinical history and comorbidities: history of hypertension, diabetes mellitus, chronic kidney disease, cerebrovascular disease, peripheral vascular disease, chronic obstructive pulmonary disease, hepatic insufficiency (Child-Pugh classification), smoking history, and alcohol consumption history.

Preoperative medication history: Record medications used within 24 hours prior to randomization that cannot be safely discontinued, including RAS inhibitors, β -blockers, calcium channel blockers, diuretics, statins, antiplatelet agents, oral hypoglycemic agents or insulin, and nonsteroidal anti-inflammatory drugs (within 48 hours before surgery).

Baseline laboratory tests: serum creatinine, eGFR (CKD-EPI formula), blood urea nitrogen, hemoglobin, platelet count, albumin, myocardial troponin I, NT-proBNP, and high-sensitivity C-reactive protein.

Surgical parameters: Type of surgery, surgical urgency, extracorporeal circulation time, aortic cross-clamping duration, minimum nasopharyngeal temperature, intraoperative red blood cell transfusion volume, intraoperative urine output, and use of vasoactive drugs during surgery.

Previous intervention history: Whether the participant received vagus nerve stimulation, auricular acupuncture, transcutaneous electrical stimulation therapy, or participated in other clinical studies within 1 month prior to enrollment.

3.3.3 Statistical Analysis Plan

All data in this study were processed using SPSS 26.0 and R 4.3.0 software.

For continuous variables, the Shapiro-Wilk normality test is first performed. Variables conforming to normal distribution are expressed as "mean \pm standard deviation," with intergroup comparisons conducted using the independent samples t-test. Variables not conforming to normal distribution are represented by median values (25th and 75th percentiles), and intergroup comparisons are performed using the Mann-Whitney U rank-sum test. Categorical variables are presented as frequencies (percentages), with intergroup comparisons analyzed using the χ^2 test. If theoretical frequencies do not meet the test requirements, the Fisher exact probability method must be employed.

The primary endpoint of this study was the incidence of AKI within 7 days postoperatively, analyzed based on the intention-to-treat principle. Kaplan-Meier curves were constructed to plot the cumulative incidence of AKI within 7 days postoperatively for both groups, with intergroup comparisons performed using the log-rank test. The Cox proportional hazards regression model was employed to estimate the hazard ratio (HR) and its 95% confidence interval for the ta-VNS group versus the sham stimulation group. A single-factor COX regression model incorporating only grouping variables was first fitted to estimate the crude effect, followed by a multivariate

COX regression model that adjusted for preoperative eGFR (<90 vs. ≥ 90 mL/min/1.73 m²), diabetes history (present vs. absent), left ventricular ejection fraction (<35% vs. $\geq 35\%$), and surgical type (high-risk group [valve and coronary artery combined/aortic surgery] vs. low-risk group [valve and septal repair]) as covariates. Under the random missingness assumption, imputation models were constructed based on covariates related to outcomes and missingness states, generating 20 imputed datasets for analysis, with results combined according to the Rubin rule. Under the non-random missingness assumption (all missing values in the ta-VNS group were AKI, while all missing values in the sham stimulation group were non-AKI), intergroup comparisons were re-evaluated.

The severity of AKI was analyzed using multivariate ordered logistic regression, adjusting for the same covariates as in the primary analysis and testing the proportional hazards assumption. Results were reported as odds ratios (OR) and their 95% confidence intervals (CI).

The proportion of patients requiring RRT during hospitalization was compared between groups using χ^2 test or Fisher's exact probability method; the duration of RRT was compared between groups based on its distribution characteristics using independent samples t-test or Mann-Whitney U test.

The proportion of patients with persistent AKI was compared between groups using the χ^2 test; the time to renal function recovery was plotted as cumulative recovery curves using the Kaplan-Meier method, with intergroup comparisons performed via the log-rank test. Patients who did not recover during the observation period were treated as censored data.

Serum creatinine and eGFR at 30 days postoperatively were compared between groups using independent samples t-test or Mann-Whitney U test based on their distribution characteristics.

HRV was analyzed using generalized estimating equations, with grouping, time points, and their interaction terms included as fixed effects. The optimal working-related matrix structure was selected based on the quasi-likelihood independence criterion. Significant group \times time interaction terms indicated statistically distinct temporal trends in HRV metrics between the two groups.

The duration of mechanical ventilation, peak/mean values of vasoactive drug index, peak/mean values of postoperative 48-hour pain NRS scores, and total opioid consumption were compared between groups using independent samples t-test or Mann-Whitney U test based on

their distribution characteristics. The incidence of delirium was compared between groups using χ^2 test. MMSE, QoR-15, and RCSQ were analyzed using generalized estimating equations (GEE), with model specifications identical to those used for HRV analysis.

The incidence rates of new-onset atrial fibrillation, pulmonary infection, stroke, and 30-day all-cause mortality were compared between groups using χ^2 test or Fisher's exact probability method. If the number of events was sufficient, Cox proportional hazards regression model could be employed for analysis, with adjustment for covariates when necessary. Hazard ratios (HR) and their 95% CI were reported.

Hospitalization duration and ICU stay duration were treated as continuous variables, which were expected to follow a skewed distribution. Between-group comparisons were performed using the Mann-Whitney U test. The re-admission rate due to complications was compared using the χ^2 test.

GEE were employed to analyze differences in the temporal variation trajectories of routine laboratory parameters and plasma IL-6/NGAL levels between two groups. The model included grouping, time, and their interaction as fixed effects, with subjects as random effects. Appropriate work-related matrices and distribution families were selected to assess the significance of the group \times time interaction. Independent samples t-test or Mann-Whitney U test was used to compare postoperative monocyte α 7nAChR expression levels, intracellular IL-6+ proportion, and Th17/Treg ratio at various time points between the two groups. GEE analysis was also conducted to evaluate overall trends and intergroup differences. Spearman correlation analysis was employed to investigate associations between immune cell markers (α 7nAChR, IL-6+, Th17/Treg), plasma biomarkers (IL-6, NGAL), and clinical outcomes (AKI incidence rate, peak serum creatinine level).

[figure not shown]
To determine the minimum number of stimulation days required to achieve clinical efficacy, the completion of stimulation was defined as when the actual daily stimulation duration reached $\geq 80\%$ of the planned duration. Based on the total number of days (0-6 days) during which subjects completed stimulation, a multivariate logistic regression analysis was performed to examine the dose-response relationship between cumulative stimulation days and the incidence of AKI, thereby identifying the critical number of days when the protective effect tends to plateau.

Subgroup analysis was conducted based on the following prespecified factors: gender, left ventricular ejection fraction (<35% vs. $\geq 35\%$), age (<65 years vs. ≥ 65 years), preoperative eGFR (<90 vs. ≥ 90 mL/min/1.73 m²), CPB duration (<120 min vs. ≥ 120 min), and surgical type (high-risk group [valve and coronary artery combined/aortic surgery] vs. low-to-moderate risk group [valve and septal repair]). Subgroup analysis was implemented in single-factor logistic regression models by introducing interaction terms between grouping and subgroup variables, with OR values and 95% CI for each subgroup visually presented in forest plots.

Safety analysis was based on the safety dataset (all subjects who received at least one stimulation). The incidence rates of all adverse events and serious adverse events were compared between groups using the χ^2 test or Fisher's exact probability method.

Unless otherwise specified, all tests were conducted as two-tailed tests with a significance level set at $\alpha = 0.05$, meaning that differences were considered statistically significant when $P < 0.05$.

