3.3 Research Content

3.3.1 Stratification, Blinding, and Intervention

After stratifying subjects according to the Cleveland Clinic scoring system for predicted dialysis-required AKI risk (high risk: ≥ 6 points vs. low-to-moderate risk: 1-5 points), independent statisticians generated computer-generated block random sequences (block size: 2 or 4) to assign participants at a 1:1 ratio to either the ta-VNS group or sham stimulation group. The grouping results were sealed in sequentially numbered opaque envelopes.

Blinding was implemented for both participants and outcome evaluators. After obtaining informed consent from participants, a non-blind study coordinator who would not be involved in subsequent clinical work publicly opened the envelope, recorded the grouping information, and handed it to a trained non-blind operator to execute the corresponding stimulation protocol. Other researchers (including those responsible for follow-up, data collection, testing, and statistical analysis) remained unaware of the grouping assignments.

The ta-VNS group received electrical stimulation via a transcutaneous auricular vagus nerve stimulator (tVNS501) applied to the left auricular cartilage. The parameters were set as follows: frequency 25Hz, pulse width 250 μ s, with a stimulation-interval cycle of 30 seconds stimulation followed by 30 seconds rest. The stimulation intensity was incrementally increased starting from 0.4V in 0.4V increments until the subject experienced pain, then adjusted downward to just below the pain threshold to determine the optimal stimulation intensity. The stimulation coverage spanned preoperative, intraoperative, and postoperative phases: beginning on the day of surgery upon entering the preoperative preparation room and continuing until the patient was transferred to the ICU, followed by 6 hours of stimulation. From postoperative days 1 to 5, the stimulation regimen was restored to twice daily (at 9:00 AM and 2:00 PM) with each session lasting 120 minutes [42-44].

In the sham-stimulation group, electrodes were placed at the same site and within the same cycle period with optimal intensity determined, but stimulation output was turned off without administering actual electrical stimulation.

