3.4 Research Flowchart

IV. Sample Size Calculation

The sample size for this study was estimated based on preliminary experimental results from our research center. In the pilot study, the incidence rates of CPB-associated AKI in the ta-VNS group and sham stimulation group were 17.1% and 37.9%, respectively. With a significance level of $\alpha = 0.05$ (bilateral) and a power of $1 - \beta = 0.80$, calculated using G*Power software (version 3.1.9.7), 68 patients were required in each group. Considering a 10% dropout rate, a total of 152 patients were enrolled in this study, with 76 patients in each group.

V. Data Management and Confidentiality

Only investigators authorized by the principal investigator are permitted to access or analyze data. Computer systems used for data management must be password-protected, and paper documentation must be locked.

All information related to the subject's identity is kept confidential, and such information shall not be disclosed beyond the scope permitted by applicable laws and/or regulations.

VI. Informed Consent

Prior to enrollment in this study, the investigator responsible for obtaining informed consent must provide each participant with a comprehensive written explanation regarding the study's objectives, nature, procedures, potential benefits, and risks. Participants should be informed of their right to withdraw from the study at any time. Before enrollment, each participant must be fully informed and given sufficient time to consider participation. Enrollment is permitted only after voluntary participation and signing of the informed consent form.

The vulnerable groups potentially involved in this study include elderly individuals and illiterate persons. If the subject is unable to read or sign the informed consent form due to lack of capacity for action, their guardian must act as proxy for the informed consent process and sign the document. If the subject lacks the ability to read the informed consent form (e.g., illiteracy), a witness must observe the informed consent process and sign the consent form.

VII. Adverse Events and Related Management Measures

ta-VNS is a selective, non-invasive, and low-risk effective VNS strategy. The primary

adverse events include pain, influenza-like symptoms, and local skin discomfort, which resolve immediately after cessation of stimulation. To date, no literature has reported serious adverse events associated with this procedure.

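### The primary analysis leaves out the randomisation stratum and does not say which result decides a trial that is defined and sized on a 7-day proportion

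*Combined protocol and SAP*

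**What the plan says.** Section 3.3.1 sets up the randomisation: "After stratifying subjects according to the Cleveland Clinic scoring system for predicted dialysis-required AKI risk", with high risk as 6 points or more and low-to-moderate risk as 1 to 5 points, in blocks of 2 or 4 at 1:1. The Cleveland Clinic score is among the baseline data to be collected before randomisation (section 3.2.2's companion list of basic clinical indicators, 3.3.2.3).

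Section 3.3.2.1 defines the primary endpoint as a proportion: "Percentage of subjects who developed new-onset AKI within 7 days postoperatively". Section IV sizes the trial on two proportions: "the incidence rates of CPB-associated AKI in the ta-VNS group and sham stimulation group were 17.1% and 37.9%, respectively", and "calculated using G*Power software (version 3.1.9.7), 68 patients were required in each group".

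For that endpoint, section 3.3.3 gives Kaplan-Meier curves with a log-rank test and then Cox models: "A single-factor COX regression model incorporating only grouping variables was first fitted to estimate the crude effect", followed by a model with eGFR, diabetes, left ventricular ejection fraction (LVEF) and surgical type. The Cleveland Clinic stratum is in none of these. After randomisation it is used only to sample the 40-patient mechanistic subset (section 3.3.2.2). On significance, section 3.3.3 says that "all tests were conducted as two-tailed tests with a significance level set at" 0.05. It does not say which analysis decides the primary hypothesis. The severity analysis refers back to the covariates of the primary analysis, which hints at the adjusted Cox model without declaring it.

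**The concern.** There are two gaps in the same paragraph.

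1. Stratified randomisation balances the arms within each risk level, so the true sampling variance of the treatment comparison is smaller than an unstratified test assumes. The unstratified test then uses a standard error that is too large, and power is lost.
2. The question asked, the endpoint and the sample size all concern the share of patients with AKI by day 7. The primary paragraph answers with a time-to-event test and hazard ratios, in crude and adjusted form, with no rule for which counts. If the two disagree, the trial's conclusion depends on which is quoted.

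Other parts of the plan already treat AKI as yes/no. The worst-case missing-data rule assigns AKI or no AKI without an event day, which a Cox model would need, and the subgroup analyses report odds ratios.

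**Working it through.** **1. The plan's own sample size.** Inputs from section IV: 17.1% and 37.9%, two-sided 0.05, power 0.80, dropout 10%. With unpooled variance:

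n = (1.960 + 0.842)² × [0.171×0.829 + 0.379×0.621] / 0.208² = 7.849 × (0.1418 + 0.2354) / 0.0433 = 68.4 per arm.

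This agrees with the stated 68 after rounding. 68/0.9 = 75.6, so 76 per arm and 152 in total. The trial is therefore sized on a difference in proportions. (With the pooled-variance test, power is 78.2% at 68 per arm and 82.6% at 76.)

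**2. Is the hazard-ratio analysis underpowered?** Under an assumed constant hazard, HR = ln(0.829)/ln(0.621) = 0.394. Schoenfeld's formula gives 4 × 7.849 / (ln 0.394)² = 36.1, so 37 events. Expected events are 68 × (0.171 + 0.379) = 37.4, or 41.8 at 76 per arm. Power is adequate. The mismatch concerns which question is answered.

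**3. Cost of omitting the stratum.** The documents give neither the high-risk share f nor the odds ratio (OR) between strata, so both are assumed. Let a and b be the AKI risks in the low and high stratum of an arm, solved so that (1−f)a + fb equals the arm's rate. Let r be the stratified variance of the risk difference divided by the unstratified variance.

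Example with f = 20%, OR 4:
- ta-VNS: a = 0.124, b = 0.361; within-stratum variance 0.8×0.124×0.876 + 0.2×0.361×0.639 = 0.133.
- Sham: a = 0.312, b = 0.645; 0.8×0.312×0.688 + 0.2×0.645×0.355 = 0.218.
- r = 0.350/0.377 = 0.929.

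At 68 per arm the planned difference is 0.208/√(0.377/68) = 2.793 unstratified standard errors. Approximate power is:
- unstratified: Φ[(2.793 − 1.960)/√0.929] = Φ(0.864) = 0.806
- stratified: Φ[2.793/√0.929 − 1.960] = Φ(0.938) = 0.826

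The gain is about 2 points.

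The same comparison was simulated with the planned log-rank test (68 per arm, balanced within stratum, 20,000 trials per row). The null uses 27.5% in both arms.

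| f | OR | r | Power, unstratified | Power, stratified | Type I, unstratified | Type I, stratified |
|---|---|---|---|---|---|---|
| 5% | 2 | 0.995 | 0.785 | 0.785 | 0.050 | 0.051 |
| 30% | 2 | 0.978 | 0.794 | 0.800 | 0.048 | 0.050 |
| 10% | 4 | 0.957 | 0.793 | 0.802 | 0.043 | 0.048 |
| 20% | 4 | 0.929 | 0.801 | 0.817 | 0.042 | 0.051 |
| 30% | 4 | 0.914 | 0.799 | 0.824 | 0.040 | 0.052 |
| 20% | 8 | 0.847 | 0.807 | 0.848 | 0.033 | 0.051 |
| 30% | 8 | 0.817 | 0.817 | 0.863 | 0.027 | 0.048 |

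Chi-square against Cochran-Mantel-Haenszel, at 68 or 76 per arm with f from 5% to 40%, gives the same picture. Unstratified type I error is about 0.028 to 0.051, against about 0.05 stratified. The power gain is about 0 to 5 points: under 1 at OR 2 and about 2.5 at most at OR 4.

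**4. Cost of not naming the deciding analysis.** Under assumed covariate effects, type I error was 0.050 for chi-square, 0.045 for crude Cox and 0.048 for adjusted Cox. If any one of the three could be called the result, it was 0.066. This is illustrative: the plan assigns chi-square to categorical variables in general and not to the primary endpoint.

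**The case against.** The strongest reply is that little is lost.

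- **Size.** Entry is limited to elective surgery, eGFR of at least 60, ASA I-III and NYHA I-III, and preoperative AKI and renal replacement therapy are addressed in the exclusions. Nothing in the documents points to a high-risk share of 30-40%. Simulating the log-rank test against a Cox model with the stratum added (152 patients, 4,000 trials) gave power of 0.832 and 0.829 at 10% and OR 2, and 0.840 and 0.854 at 30% and OR 4. Only 30% and OR 8 gave a clear gap (0.862 and 0.898). This stands.
- **Adjusted model.** Its four covariates may carry part of the stratum's information. The documents do not list the score's components, so this cannot be checked.
- **Number of tests.** A reader might infer three competing tests. The log-rank test is the score test of the group-only Cox model, and the two disagreed at 0.05 in 1% of simulated trials or fewer. The real choice is unadjusted against adjusted. This stands too.
- **Roles and display.** The plan uses log-rank to compare and Cox to estimate, and the Kaplan-Meier curves show cumulative incidence to day 7. That narrows the gap, but the curves come with no risk difference or risk ratio, and neither Cox result is declared primary.

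**Conclusion.** The point holds as an improvement that should be made, not as a flaw that threatens validity. The stratum is missing from every primary comparison, the choice between unadjusted and adjusted results is open, and the sized proportion has no specific test or effect measure. These follow from the text and are certain. The power loss of about 0 to 5 points is not certain, because it rests wholly on the assumed high-risk share and stratum strength.

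Three stronger readings are not supported:
- That the unstratified test inflates false positives: its error rate falls at or below nominal, apart from simulation noise.
- That the trial is underpowered because it uses hazard ratios: about 37 events are needed and about 37 to 42 expected.
- That cutting eGFR and LVEF in two is an error: it is a modelling choice whose cost has not been quantified here.

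The precision gain applies to the risk difference. For a hazard ratio, which is non-collapsible, adjustment shows up as power and not necessarily as a narrower interval.

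As written, a score of 0 belongs to neither stratum. Whether 0 can occur depends on a score definition that the documents do not give.

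**What to change.** In section 3.3.3:

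1. Declare one primary analysis: AKI by day 7 (yes/no) in all randomised patients, stratified by the Cleveland Clinic stratum (for example Cochran-Mantel-Haenszel), with risk difference and risk ratio and 95% confidence intervals.
2. State how it combines across the 20 imputed datasets: pool the stratified estimate and its variance with Rubin's rules (the risk ratio on the log scale).
3. Label Kaplan-Meier, log-rank and Cox as supportive, and stratify the log-rank test and the Cox models by Cleveland Clinic risk.
4. Bring the stratum into the adjusted model and keep all planned covariates, including surgical type. With about 37 events and 5 coefficients there are about 7.5 events per coefficient (37.4/5), or 6.2 (37.4/6) if the stratum is a covariate. Stratifying the baseline hazard spends no coefficient.
5. Ask the sponsor to confirm whether a score of 0 can occur and, if so, to assign it to a stratum in section 3.3.1.

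The cost is wording only. The score is already collected before randomisation, and neither the sample size nor any procedure changes.
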